#### **9.1.2. Prior Tumor Necrosis Factor (TNF) Antagonist History**

Data on prior use of anti-TNF agents administered to patients will be collected separately in the “Prior TNF Antagonist History” eCRF. The same rules for date imputation and definitions of prior and concomitant will apply. A table will be produced showing total number of prior TNF antagonists used and the number and percentage of patients with at least one prior TNF antagonist use who had prior use of TNF antagonists. Summaries will be based on the safety

population and safety population – Extension Study Period subset and presented by treatment group and part.

A listing of prior TNF antagonist history will be presented by treatment group for the safety population. The antagonist name, drug class, and PT, single dose, unit, frequency, route, start date, stop date and reason for discontinuation will be included for each patient.

## 9.2. Exposure to Study Drug

The number and percentage of patients with full and partial dose administered at each visit will be tabulated. For patients who are not administered study drug, the number and percentage of patients with each reason why the dose was not administered (discontinued prior to visit, adverse event, other, monitoring) will be displayed. For patients who administered study drug and total dose administered (mg) will be summarized by part, visit and treatment group. The safety population and safety population – Extension Study Period subset will be used as the denominator for percentages and patients will be summarized.

In a separate analysis, the total number of doses received by each patient during study period will be calculated. A table will be provided displaying descriptive statistics of the total number of doses received and total amount of study drug administered. Summaries will be based on the safety population and safety population – Extension Study Period subset and presented by treatment group and part.

In addition, a listing will be provided by treatment group for the safety population showing the details of study drug exposure for each patient. This listing will include all data collected on the study treatment infusion page of the eCRF.

## 10. Pharmacokinetics

Co-Primary PK endpoints are  $AUC_{0-last}$ ,  $AUC_{0-\infty}$  and  $C_{max}$  over the first 24 weeks in the Part 1. The secondary PK endpoints are as below.

- Part 1 (over the first 24 weeks):  $AUC_{0-day14}$ ,  $V_d$ ,  $CL$ ,  $t_{1/2}$ ,  $T_{max}$ ,  $C_{max,1}$ ,  $C_{min}$  (at Week 24) and  $C_{trough}$
- Part 2 (up to Week 48 or over the first 24 weeks if second course of treatment is not administered):  $T_{max}$ ,  $C_{max}$ ,  $C_{max,1}$ ,  $C_{min}$  and  $C_{trough}$

All pharmacokinetic analysis will be performed on the PK population and PK – 2nd treatment course in Main Study Period subset unless otherwise specified. Descriptive Statistics regarding the PK parameters will be performed by including outliers.

### 10.1. Serum concentrations

Pharmacokinetic samples will be listed for the safety population by each patient and sampling time point:

For Part 1, pharmacokinetic samples will be collected within 15 minutes prior to the beginning of the study drug infusion, within 15 minutes after the end of study drug infusion, and 1 hour ( $\pm 15$  minutes) after the end of study drug infusion on the day of each study drug infusion. For patients from Part 1 who receive only first course of treatment, additional samples will be collected after 24 hours ( $\pm 2$  hours) from the start of each study drug infusion in the first treatment course and on Week 1, 3, 4, 8, 12, 16 and 24, 15 samples in total. For patients from Part 1 who receive both

first and second courses of treatment, additional samples will be collected after 24 hours ( $\pm 2$  hours) from the start of each study drug infusion only in the first treatment course and on Week 1, 3, 4, 8, 12, 16, 48 and end of study (EOS; if patient withdraws prior to study completion), 21 samples in total.

For Part 2, pharmacokinetic samples will be collected within 15 minutes prior to the beginning of the study drug infusion, within 15 minutes after the end of study drug infusion, and 1 hour ( $\pm 15$  minutes) after the end of study drug infusion on the day of each study drug infusion. Additional samples will be collected on Week 24 (for patients who receive only first course of treatment) or Week 48 (for patients who receive both first and second courses of treatment) or EOS (for patients who receive both first and second courses of treatment and if patient withdraws prior to study completion).

Serum concentrations of rituximab will be summarized using descriptive statistics (consisting of n, mean, SD, CV, geometric mean, minimum, median and maximum) by part and treatment group at each scheduled collection visit and time point. Additionally, serum concentrations of rituximab for all antibody negative and positive subjects will be summarized by study part and treatment group at each scheduled collection visit and time point. In case of patients from Part 2, Combined Rituxan and MabThera group will be additionally displayed. Individual concentrations, scheduled and actual sample times will be presented in data listings by treatment group for the safety population.

Concentrations below the limit of quantification (BLQ) prior to the first infusion will be treated as zero (0). Concentrations BLQ after the first infusion will be set to the lower limit of quantification (LLoQ, 0.04  $\mu\text{g/mL}$ ). Mean BLQ concentrations will be presented as BLQ, and the SD and CV will be reported as not applicable. Geometric mean will not be reported if the dataset includes zero values.

For patients from Part 1, mean serum concentration versus actual time plots for rituximab will be presented up to Week 24. Plots will be presented on both linear and semi-logarithmic scales by treatment based on scheduled sample times. All BLQ and missing values will be indicated in the data listings. In addition, plots will be presented by ADA status at Week 24.

## 10.2. Pharmacokinetic Parameters

Individual serum concentration versus actual time data will be used to calculate PK parameters of rituximab by standard non-compartmental methods using [REDACTED]. All serum concentrations that are BLQ prior to the first infusion will be set to 0; all concentrations below LLoQ after first infusion will be set equal to LLoQ. Actual blood sampling times (from the start of infusion) and actual duration of the infusion will be used for all PK analyses. However, for ease of presentation, scheduled sampling times will be used to present results in summary tables and figures.

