7.8.1.1 Co-primary Pharmacokinetic Analysis

The primary PK analysis will assess the similarity of CT-P10, Rituxan and MabThera in terms of AUC_{0-last} (over both infusions of the first course of treatment, from time zero to the last measurable concentration), $AUC_{0-\infty}$ (over both infusions of the first course of treatment, from time zero to infinity) and C_{max} (after the second infusion of the first course of treatment) as co-primary PK endpoints.

The following PK parameters as co-primary PK endpoints will be calculated using noncompartmental methods:

- AUC_{0-last} will be calculated using trapezoidal rule. This will be calculated over both infusions in the first course of treatment.
- AUC_{0-∞} will be calculated using trapezoidal rule. This will be calculated over both infusions in the first course of treatment.
- C_{max} will be calculated after the second infusion in the first course of treatment.

In each part, for the calculation of PK parameters, all serum concentrations that are below the quantification limit (BQL) prior to the first measurable concentration will be set to zero. The BQL values after the first dose will be set equal to the lower limit of quantification. Actual sampling times, rather than scheduled sampling times, will be used in all computations of PK parameters.

- The primary PK parameter estimates will be analysed using an analysis of covariance (ANCOVA) with treatment as a fixed effect and country, gender, race, prior anti-TNFalpha (anti-TNF α) blocker status (inadequate response versus intolerant case), and RF or anti-CCP status (both positive versus both negative versus either RF or anti-CCP negative) fitted as covariates. If country is found to be unsuitable as a covariate due to the number of levels, then this may be pooled into a new variable, region defined in the SAP, for use as a covariate. Point estimates (geometric means and ratio of geometric means) will be calculated from back transforming the least squares means of the natural log-transformed values of AUC_{0-last}, AUC_{0- ∞} and C_{max}, and 90% CIs for the ratio of the geometric means of the 2 treatments (CT-P10 versus Rituxan, CT-P10 versus MabThera, and Rituxan versus MabThera) will also be produced. AUC_{0-last}, AUC_{0- ∞}, and C_{max} will be summarized by treatment. Summary statistics will include the mean, SD, median, minimum, maximum, geometric mean, and CV.

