**Table 2: Pharmacokinetic Parameters for Rituximab**

Part 1 Primary Parameters (calculated over the first 24 weeks)	
AUC 0-last	Area under the concentration-time curve from time 0 to the last measurable concentration over both doses of the first course
AUC 0-∞	Area under the concentration-time curve from time 0 extrapolated to infinity over both doses of the first course

$C_{max}$	Observed maximum concentration after the second infusion
Part 1 Secondary Parameters (calculated over the first 24 weeks)	
$AUC_{0-day14}$	Area under the concentration-time curve from time 0 to Day 14 (calculated for both infusions)
$C_{max, 1}$	Observed maximum concentration following the first infusion of the first course
$C_{min}$	Predose concentration at Day 168 (Week 24)
$C_{trough}$	Predose concentration at Day 14 (Week 2) prior to the second infusion
$V_d$	Volume of distribution, calculated from the second dose of the first course as $V_d = \text{Dose}/AUC_{0-\infty} \times \lambda_z$ , where Dose is the combined total dose administered in Course 1 (i.e. Dose 1 + Dose 2)
CL	Total clearance, calculated from the second dose of the first course as $CL = \text{Dose}/AUC_{0-\infty}$ , where Dose is the combined total dose administered in Course 1 (i.e. Dose 1 + Dose 2)
$t_{1/2}$	Terminal phase elimination half-life, calculated from the second dose of the first course as $t_{1/2} = \ln(2)/\lambda_z$
$T_{max}$	Time to maximum serum concentration after both doses in the first course
Part 2 Secondary Parameters (up to Week 48 or over the first 24 weeks if second course of treatment is not administered)	
$T_{max}$	Time to maximum serum concentration in the first and second course
$C_{max}$	Observed maximum concentration after the second infusion in the first and second course
$C_{max, 1}$	Observed maximum concentration after the first infusion of the first and second course
$C_{min}$	Predose concentration at Day 168 (Week 24) and at Day 336 (Week 48)
$C_{trough}$	Predose concentration at Day 14 (Week 2 prior to second infusion) and at Day 182 (Week 26 prior to second infusion)

All AUC parameters will be calculated using the linear trapezoidal rule.

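### Replacing every post-dose BLQ concentration with the LLoQ conflicts with the AUC0-last definition and can lengthen reported half-life in fast eliminators; the co-primary conclusion is not at risk

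*SAP*

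**What the plan says.** The rule appears in three places. SAP 10.1, on serum concentrations, states: "Concentrations BLQ after the first infusion will be set to the lower limit of quantification (LLoQ, 0.04" ug/mL). SAP 10.2 repeats it for the noncompartmental parameter calculation: "all concentrations below LLoQ after first infusion will be set equal to LLoQ". Protocol 7.8.1.1 does the same: "The BQL values after the first dose will be set equal to the lower limit of quantification". In both documents BLQ values before dosing become zero.

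SAP Table 2 defines the co-primary AUC0-last as "Area under the concentration-time curve from time 0 to the last measurable concentration over both doses of the first course"; protocol 7.1.1 and 7.8.1.1 also end it at the last measurable value. Below the table the SAP adds "All AUC parameters will be calculated using the linear trapezoidal rule".

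Two Part 1 secondary parameters in Table 2 use lambda-z:
- Half-life: "Terminal phase elimination half-life, calculated from the second dose of the first course as" ln(2)/lambda-z.
- Vd: "Volume of distribution, calculated from the second dose of the first course as" Dose/AUC0-inf x lambda-z, as printed.

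Neither document says which points enter the lambda-z fit, sets a minimum number of points or a goodness-of-fit criterion, or exempts trailing BLQ values.

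**The concern.** A trailing BLQ sample is by definition not measurable. Once it carries the value 0.04, software that takes the last positive concentration as the end of the profile will run AUC0-last to Week 24. That contradicts the endpoint's own definition.

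The second effect is on the terminal slope. The true concentration lies below 0.04, so the substitution raises the last point or points and flattens the log-linear fit. Lambda-z falls, and half-life and the extrapolated part of AUC0-inf rise. Vd rises too under the usual formula. The patients concerned are those who eliminate fastest. At stake are two listed secondary parameters and the consistency of a co-primary definition. The co-primary result itself is not.

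**Working it through.** The documents give no figure for this effect. The nearest is the Part 1 power of 96.5% per comparison, which reproduces. The log SD is sqrt(ln(1 + 0.30^2)) = 0.294 and SE = 0.294 x sqrt(2/50) = 0.0587. Then 2 x Phi(0.2231/0.0587 - 1.645) - 1 = 96.9%, or 96.7% on the t distribution.

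**Inputs from the documents.** LLoQ 0.04 ug/mL (SAP 10.1). Expected peak about 400 ug/mL, SD 200, and half-life about 20 days with an SD of several days; 20.8 days is cited for MabThera (protocol section 1). Part 1 samples after the Day 14 infusion: end of infusion, 1 h, 24 h, then Days 21, 28, 56, 84, 112 and 168 (protocol Table 7).

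**Assumptions.** Mono-exponential decline; for the shares, a normal distribution of half-life around 20 days.

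**Who has a BLQ value.** Day 14 to Day 168 is 154 days. Week 24 is BLQ when half-life < 154 x ln 2 / ln(400/0.04) = 106.7/9.21 = 11.6 days (12.5 and 11.1 days for peaks of 200 and 600). Weeks 16 and 24 are both BLQ below 98 x ln 2 / 9.21 = 7.4 days. At 20.8 days the Week 24 value is 400 x 2^(-154/20.8) = 2.4 ug/mL, roughly 60 times LLoQ.

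**Slope, true half-life 8 days, last three points.** Model values at Days 84, 112 and 168 are 0.929, 0.0821 and 0.0006 ug/mL; the last becomes 0.04. The logs are -0.074, -2.500 and -3.219. Deviations from the mean day are -37.33, -9.33 and 46.67. Slope = (2.75 + 23.33 - 150.21)/3658.7 = -0.0339, so the reported half-life is 0.693/0.0339 = 20.4 days. Without the BLQ value it is 8.0.

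The same regression on other point sets, with a single 400 ug/mL peak at Day 14:

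| True half-life (d) | Days 15-168 | Days 28-168 | Last three | BLQ dropped |
|---|---|---|---|---|
| 11 | 11.5 | 11.6 | 12.2 | 11.0 |
| 10 | 11.2 | 11.7 | 13.7 | 10.0 |
| 8 | 10.7 | 11.8 | 20.4 | 8.0 |

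Adding residual drug from the first infusion changes the 8-day row to 10.4, 11.5 and 18.6. Selecting points by best adjusted R2 also gives 10.4. Vd as Dose/(AUC0-inf x lambda-z) follows: 2.25 L with the BLQ value dropped, against 2.93 L (best fit) or 5.20 L (last three).

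**Share of patients.** P(half-life < 11.6) with mean 20 is 0.3% at SD 3, 1.8% at SD 4, 4.6% at SD 5 and 11.5% at SD 7. P(half-life < 8) is only 0.8% at SD 5 and 4.3% at SD 7.

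**Co-primary AUCs.** Under log-linear decline, substituting rather than dropping changes AUC0-last by 0.35% or less (at 5 days, 6623.0 against 6599.8 ug*day/mL) and AUC0-inf by 0.25% or less.

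**The case against.** The passages can be read together: an imputed value is not a measurable one, so an analyst could still stop AUC0-last at the last real observation. Nothing states that imputed points enter lambda-z. The SAP refers only to standard noncompartmental methods, and BLQ values are flagged in the listings, so they can be found and excluded. This stands in part. The bias is conditional. But the rule is written for parameter calculation with no exception, so following it literally puts the values into the data set from which lambda-z is fitted.

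The Vd direction depends on how Table 2 is read. Taken left to right, the printed expression would fall rather than rise. That reading does not have the units of a volume, so lambda-z in the denominator is the likely intent, but it remains an assumption.

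Dropping BLQ values is not always better. In a modelled profile whose half-life shortens from 18 to 5 days at Day 112, the fit to the true values gives 6.3 days, substitution 8.0 and dropping 18.0. Dropping also lowers AUC0-last by 1.9% (21391.7 against 21801.4). This stands as a limit on the fix.

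A reader might infer that 5 to 12% of patients would have half-lives inflated to 12 to 30 days. That joins two different groups: those shares cover everyone below 11.6 days, while the large inflation appears at 7 to 8 days, and the upper end needs a last-three-points rule that the SAP does not contain.

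**Conclusion.** The point holds, at minor severity. A stated rule conflicts with the definition of a co-primary parameter and, where imputed values reach lambda-z, overstates half-life and probably Vd. The size rests on mono-exponential decline from about 400 ug/mL, on the points chosen for lambda-z, and on the spread of half-life, which the protocol gives only as several days. A typical patient is unaffected.

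Two stronger readings are tempting and unsupported:
- **That PK similarity is in doubt.** The AUC changes are far too small to matter against 80-125%.
- **That the rule hides an effect of anti-drug antibodies.** Neither document says ADA-positive patients eliminate faster, so any effect on the half-life and Vd summaries by ADA status is conditional on that. Even then, CL (Dose/AUC0-inf), the AUCs, and the concentrations and plots by ADA status are essentially untouched. A true 8 days reported as 10.4 would still be about half the expected 20.

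**What to change.** In SAP 10.2, for parameter derivation:
- Set BLQ values before the first infusion to zero.
- Define Tlast as the last sample at or above LLoQ, and exclude later BLQ values from AUC0-last and lambda-z.
- Require at least three quantifiable points and a stated minimum adjusted R2 for lambda-z; report half-life, Vd and AUC0-inf as not estimable when unmet.
- Print the Vd denominator with brackets.

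Keep LLoQ substitution for concentration summaries only. Protocol 7.8 requires changes from its planned analyses to be documented in the SAP, so record the departure from 7.8.1.1 there.

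The cost is a short paragraph and a software setting; no new data are needed. A few patients may lose lambda-z-based parameters. If elimination accelerates late, dropping BLQ values can itself overstate half-life and slightly lower AUC0-last. The acceptance criteria would not catch the Day 112 profile, because its adjusted R2 after dropping is 1.00. Patients with trailing BLQ values should therefore be identifiable in the parameter listing.

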**Table 2: Pharmacokinetic Parameters for Rituximab**

Part 1 Primary Parameters (calculated over the first 24 weeks)	
AUC 0-last	Area under the concentration-time curve from time 0 to the last measurable concentration over both doses of the first course
AUC 0-∞	Area under the concentration-time curve from time 0 extrapolated to infinity over both doses of the first course

$C_{max}$	Observed maximum concentration after the second infusion
Part 1 Secondary Parameters (calculated over the first 24 weeks)	
$AUC_{0-day14}$	Area under the concentration-time curve from time 0 to Day 14 (calculated for both infusions)
$C_{max, 1}$	Observed maximum concentration following the first infusion of the first course
$C_{min}$	Predose concentration at Day 168 (Week 24)
$C_{trough}$	Predose concentration at Day 14 (Week 2) prior to the second infusion
$V_d$	Volume of distribution, calculated from the second dose of the first course as $V_d = \text{Dose}/AUC_{0-\infty} \times \lambda_z$ , where Dose is the combined total dose administered in Course 1 (i.e. Dose 1 + Dose 2)
CL	Total clearance, calculated from the second dose of the first course as $CL = \text{Dose}/AUC_{0-\infty}$ , where Dose is the combined total dose administered in Course 1 (i.e. Dose 1 + Dose 2)
$t_{1/2}$	Terminal phase elimination half-life, calculated from the second dose of the first course as $t_{1/2} = \ln(2)/\lambda_z$
$T_{max}$	Time to maximum serum concentration after both doses in the first course
Part 2 Secondary Parameters (up to Week 48 or over the first 24 weeks if second course of treatment is not administered)	
$T_{max}$	Time to maximum serum concentration in the first and second course
$C_{max}$	Observed maximum concentration after the second infusion in the first and second course
$C_{max, 1}$	Observed maximum concentration after the first infusion of the first and second course
$C_{min}$	Predose concentration at Day 168 (Week 24) and at Day 336 (Week 48)
$C_{trough}$	Predose concentration at Day 14 (Week 2 prior to second infusion) and at Day 182 (Week 26 prior to second infusion)

All AUC parameters will be calculated using the linear trapezoidal rule.

The pharmacokinetic parameters will be presented for the PK population in listings and summarized in tables. The tables will display the following descriptive statistics by part: n, mean, SD, CV, geometric mean, minimum, median and maximum. In addition, descriptive statistics of PK parameter by ADA status at Week 24 will be presented.

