CT-P10 is being developed by CELLTRION, Inc. as a biosimilar candidate of Rituxan and MabThera, a compound with established efficacy in the treatment of active RA (MabThera 2015; Rituxan. 2014). Rituximab is approved as Rituxan in the United States and as MabThera in other countries. CT-P10 can offer a more affordable treatment for RA than the originator protein if similar efficacy and safety are demonstrated and allow increased access to this valuable drug with a proven mechanism of action in RA patients.

The pharmacokinetic (PK) profile is expected to be similar to that of Rituxan and MabThera. There will be 2 serum peaks of CT-P10 at the end of the IV infusions that will be

administered on Day 0 and Day 14: the peak concentrations will be approximately 400 μ g/mL with a standard deviation (SD) of $\pm 200 \mu$ g/mL. Serum levels will decrease slowly after maximum serum concentration (C_{max}) has been reached. The terminal elimination half-life (t_{1/2}) of CT-P10 is expected to be approximately 20 days (SD of \pm several days).

This is a similarity study that consists of 3 parallel arms of Rituxan (US-licensed), MabThera (EU-approved), and CT-P10. All statistical assessments will be direct comparisons between the treatment groups at corresponding time points.

The PK sampling time design is based on mean MabThera $t_{1/2}$ of approximately 20.8 days in patients with RA (MabThera 2015) and on published PK studies (Breedveld et al 2007; Tran et al 2010). The area under the concentration-time curve from time zero to time of last quantifiable concentration (AUC_{0-last}), the area under the concentration-time curve from time zero to infinity (AUC_{0- ∞}) and C_{max} (after the second infusion) from the first course of treatment were selected as the co-primary PK endpoints.

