5.2 Treatments Administered

Three courses of treatment may be administered to each patient. Each course consists of 2 infusions of study drug (1000 mg CT-P10, Rituxan or MabThera) with a 2-week interval between the first and second infusion. The first course will be an infusion of study drug at Week 0 and Week 2. If patients meet the predefined safety criteria, patients will be retreated with subsequent courses of study drug (2 infusions in each course with a 2-week interval) at the investigator's discretion.

In the Main Study Period, a visit window is not permitted from Day 0 to Day 21 (study drug may continue after discussion with the sponsor if a deviation occurs). A visit window of ± 3 days is allowed from Week 4 to Week 24, and a visit window of ± 5 days is allowed thereafter, including the EOS Visit. If patients receive the second course of infusion, the first infusion will be administered at Week 24 with a visit window of ± 3 days and the second infusion should be administered after 2 weeks (14 days) from the first infusion. A visit window is not permitted on the day of second infusion in the second course of treatment (study drug may continue after discussion with the sponsor if a deviation occurs).

The third course of treatment will be initiated between Week 48 and Week 52 of the Entire Study Period if patients become eligible according to the predefined safety criteria for the course based on the results assessed within 8 weeks from the Extension Week 0. A visit window is not permitted on the day of second infusion for the third course of treatment (study drug may continue after discussion with the sponsor if a deviation occurs).

Unscheduled visit(s) can be conducted for assessment of safety criteria until the initiation of the third course of treatment.

For both Main and Extension Study Periods, visit days during the each course of treatment will be calculated based on the date of the first infusion in the each course of treatment.

DO NOT ADMINISTER STUDY DRUG AS AN IV PUSH OR BOLUS.

The first and second infusions in each course of treatment in the Study will be administered at different infusion rates, as follows:

- First infusion: Initiate infusion at a rate of 50 mg/hour. In the absence of an infusion or hypersensitivity reaction, increase infusion rate by 50 mg/hour increments every 30 minutes, to a maximum of 400 mg/hour.

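### SAP Table 2 prints the volume-of-distribution formula without brackets; read as printed it gives CL × λz, which is not a volume

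*SAP*

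**What the plan says.** Vd is a secondary PK endpoint for Part 1 (Protocol 7.1.2; SAP section 10). The Protocol gives no formula for it. The only definition is the Vd row of SAP Table 2, which begins "Volume of distribution, calculated from the second dose of the first course as", prints "V_d = \text{Dose}/AUC_{0-\infty} \times \lambda_z", and adds "where Dose is the combined total dose administered in Course 1", that is, Dose 1 plus Dose 2.

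Two other rows of that table bear on the point:

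- CL is Dose/AUC0-∞, with the same combined dose.
- The half-life is "t_{1/2} = \ln(2)/\lambda_z", so λz is a rate with units of 1/time.

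On method, SAP 10.2 states that individual concentration data "will be used to calculate PK parameters of rituximab by standard non-compartmental methods using" a package whose name is redacted. Protocol 7.8 likewise calls for validated noncompartmental software.

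**The concern.** A table of parameter definitions is what a programmer or a QC reader works from. Here the row labelled as a volume carries an expression that, taken literally, is not one. It uses clearance multiplied by the elimination rate where a terminal-phase volume needs clearance divided by it.

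This would be more than a scale factor common to all arms. Under the printed form an arm with a longer half-life shows a smaller Vd; under the correct form it shows a larger one. In a three-arm similarity study that summarises Vd by treatment group and by ADA status, a table built on the printed form could point the wrong way.

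**Working it through.** **No figure to reproduce.** The documents state no value for Vd, CL, AUC0-∞ or λz. The check is therefore dimensional, followed by the ratio of the two readings.

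**Inputs**

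- Vd, CL and t1/2 formulas and the combined dose: SAP Table 2.
- Dose: 2 × 1000 mg = 2000 mg per course (Protocol 5.2: "Each course consists of 2 infusions of study drug (1000 mg CT-P10, Rituxan or MabThera").
- MabThera half-life: "of approximately 20.8 days in patients with RA" (Protocol, Introduction).
- CT-P10 half-life: "of CT-P10 is expected to be approximately 20 days" (same place).

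**Step 1: units.** CL = Dose/AUC0-∞ is mass ÷ (mass/volume × time) = volume/time. λz is 1/time.

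- As printed: (Dose/AUC0-∞) × λz = CL × λz, in volume/time².
- With the denominator bracketed: Dose/(AUC0-∞ × λz) = CL/λz, in volume.

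**Step 2: notation elsewhere in the SAP.** The percentage-change note in SAP 11.1.1 and the percent-agreement formulas in SAP 13.7.2 have the form a/b × 100, which can only mean (a/b) × 100. The same convention applied to the Vd row gives CL × λz.

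**Step 3: ratio of the two forms.** (CL/λz) ÷ (CL × λz) = 1/λz² = (t1/2/ln 2)². Dose and AUC cancel.

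| t1/2 | λz per day | Ratio, time in days |
|---|---|---|
| 20 days | 0.03466 | (20/0.6931)² = 832.5 |
| 20.8 days | 0.03332 | (20.8/0.6931)² = 900.5 |
| 14 to 26 days (assumed spread) | 0.04951 to 0.02666 | 408 to 1407 |

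At 20.8 days the ratio is about 18.4 with time in weeks and about 519,000 with time in hours. A valid formula for a volume would not change with the time unit, so this instability is itself a sign of the fault.

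**Step 4: illustration.** The AUC is an assumption: 5000 to 10000 µg·day/mL, with 2000 mg and 20.8 days.

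- CL = 2000/5000 to 2000/10000 = 0.4 to 0.2 L/day.
- Bracketed form: 0.4/0.03332 to 0.2/0.03332 = 12.0 to 6.0 L.
- Printed form: 0.4 × 0.03332 to 0.2 × 0.03332 = 0.0133 to 0.0067 L/day².

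**Step 5: direction.** Assume equal CL in two arms and a half-life 10% longer in one. The correct Vd ratio is 1.10. The printed form gives 1/1.10 = 0.91. The two differ by a factor of 1.10² = 1.21, whatever the time unit.

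**The case against.** The best defence is that this is shorthand. If everything after the slash is taken as the denominator, the row is correct. With the CL and half-life definitions alongside and the row labelled a volume, only that reading makes sense. The text also comes from a PDF table cell, so a flattened fraction or lost bracket cannot be ruled out. Calculation is by standard noncompartmental software, Vd has no test or margin, and a reader could recover it from the CL and half-life rows as CL × t1/2/ln 2.

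Much of this stands. The intended formula is very probably the bracketed one, and use of standard software lowers the practical risk. It does not remove the point: the row as it reads follows the SAP's own convention to the wrong answer, brackets survive in other SAP formulas, and no other passage supplies a Vd definition to settle it.

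A reader might go further and infer that Vd will be reported wrong by 900-fold. The documents do not support that. The two readings have different units, so there is no single fold-error; 900 belongs to one half-life with time in days, and Table 2 fixes no time unit for λz or AUC.

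Nor does the combined-dose instruction show that the software would reproduce the error. It changes the dose input, not the operator between AUC0-∞ and λz. Nothing says that Vd will be hand-coded from Table 2.

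**Conclusion.** The concern holds as a fault in the written definition: as printed, Vd is CL × λz, which is not a volume, reverses the dependence on λz, and does not fit with the CL and half-life rows beside it. The size is 1/λz², about 830 to 900 with time in days at half-lives of 20 to 20.8 days. This rests on reading the expression in normal operator order and on the extracted text being faithful to the page.

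The consequence is small. Vd is descriptive (Protocol 7.8.1.2; SAP 10.2). The co-primary comparisons use AUC0-last, AUC0-∞ and Cmax (SAP 10.3), and the DAS28 analysis uses no PK parameter. A wrong Vd in the outputs is possible if the row is followed literally, but it is not demonstrated.

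**What to change.** In SAP Table 2 write Vd = (Dose 1 + Dose 2)/(AUC0-∞ × λz), and state the time unit used for λz and AUC. Confirm that the programmed or software derivation matches; a quick check is that each patient's Vd equals CL × t1/2/ln 2. The cost is one pair of brackets, a unit label and one programming check. No data, sample size or other analysis changes.
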